8.4.6. Adverse Events of Special Interest

Selected nonserious and SAEs will be reported as AESIs. AESIs that also meet the definition of an SAE must be reported as described in [Section 10.3](#).

Adverse events of special interest for this study include:

- Adverse events consistent with urinary retention
 - An **AE of urinary retention** should only be recorded when a subject has a raised PVR that requires intervention with clean intermittent catheterization (CIC) or temporary placement of a urinary catheter **in addition to** one of the following criteria:
 - a) subject has a PVR of ≥ 300 mL (regardless of symptoms),
OR
 - b) subject has a PVR ≥ 200 mL and < 300 mL **and** the subject reports associated symptoms, ie, sensation of bladder fullness or inability to void despite persistent effort, that in the investigator's opinion require CIC.
- Adverse events suggestive of cystitis or urinary tract infection (UTI)
 - An **AE of UTI** will be recorded if **both** the following criteria are fulfilled, regardless of subject symptoms:
 - a) a positive urine culture result with a bacteriuria count of $\geq 10^5$ CFU/mL (ie, 100×10^3 CFU/mL)
AND
 - b) leukocyturia of ≥ 5 /hpf

If a subject meets the criteria for the definition of a UTI, the investigator will record whether the UTI was “**symptomatic**” or “**asymptomatic**” on the AE eCRF.

Note: If urinalysis/culture results are reported which, in the opinion of the investigator, are considered clinically significant but do not fulfill the above definition of a UTI, the findings should be recorded as AEs (eg, bacteriuria, leukocyturia).

- Potential major cardiac and cerebrovascular events, including death (or any event with fatal outcome), myocardial infarction, cerebrovascular accident, hospitalization for unstable angina or chest pain, hospitalization for heart failure requiring hospitalization, and coronary revascularization/angioplasty/stent
- Hypertension: An AESI of **Hypertension** (or **Worsening Hypertension**, if the subject has history of hypertension) should be recorded if any of the following three criteria are met (regardless of clinical significance):
 - For subjects with systolic blood pressure < 140 mmHg **AND** diastolic blood pressure < 90 mmHg at **baseline** (Visit 3):
The average of 3 systolic blood pressures \geq 140 mmHg **or** diastolic blood pressures \geq 90 mmHg (or both) at **any 2 consecutive visits** after baseline (Visit 3)

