10.2. Appendix 2: Clinical Laboratory Tests

The tests detailed in [Table 4](#) will be performed by the central laboratory chosen by the Sponsor. Subjects do not need to fast prior to laboratory testing. A sample for urinalysis (including microscopy for RBCs, WBCs, epithelial cells, and bacteria) and urine culture will be sent to the central laboratory only if the urine dipstick tests positive for the presence of leukocytes, nitrites, or blood cells. If a subject reports symptoms suggestive of a urinary tract infection at any visit, a urine dipstick should be performed as needed, and a sample will be sent out for urinalysis and culture, and sensitivity testing.

Table 4 Clinical Laboratory Tests

Hematology	Chemistry	Urinalysis ^a	Other
Hematocrit	Albumin	Blood	PSA ^d
Hemoglobin	Alkaline phosphatase	Glucose	Coagulation INR/PT/APTT ^e
Platelet count	ALT	Protein	
WBC (total and differential)	AST	Specific gravity	
RBC	Bicarbonate	Microscopic exam (RBCs, WBCs, epithelial cells, and bacteria)	
	Calcium	pH	
	Chloride	Color	
	Creatinine ^b		
	Glucose (fasting or non-fasting)		
	Potassium		
	Sodium		
	Total bilirubin		
	Direct bilirubin ^c		
	Blood urea nitrogen		
	Total cholesterol		

ALT = alanine aminotransferase; APTT = activated partial thromboplastin time; AST = aspartate aminotransferase; eGFR = estimated glomerular filtration rate; INR = international normalized ratio; PSA = prostate-specific antigen; PT = prothrombin time; RBC = red blood cell count; WBC = white blood cell count

^a A sample for urinalysis and urine culture/sensitivity will be sent to the central laboratory only if the urine dipstick performed at the site is positive for the presence of leukocytes, nitrites, or blood cells.

^b eGFR will be calculated and reported by the central lab.

^c If total bilirubin is elevated above the upper limit of normal.

^d PSA performed by central laboratory at Screening.

^e Only upon request from Principal Investigator (if ALT, AST and bilirubin are increased).

10.3. Appendix 3: Adverse Events: Definitions and Procedures for Recording, Evaluating, Follow-up, and Reporting

Definition of an AE

AE Definition

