- Treatment-Related TEAE of Special Interest;
- Non-fatal TEAEs;
- Hypertension TEAEs by Pre-existing Hypertension (Yes vs No) and Baseline Hypertension (Yes vs. No). Hypertension TEAEs will be selected as any TEAE with preferred term of Hypertension.
- Non-serious TEAEs occurring in 2% or more of any treatment group.

In addition, a summary of all TEAEs by PT occurring in at least 2% of subjects in the vibegron arm and greater than the placebo arm will be created and sorted by descending frequency in the vibegron arm.

Adverse events of special interest for this study include:

- Adverse events consistent with urinary retention
- Adverse events suggestive of cystitis or urinary tract infection (UTI)
- Potential major cardiac and cerebrovascular events, including death (or any event with fatal outcome), myocardial infarction, cerebrovascular accident, hospitalization for unstable angina or chest pain, hospitalization for heart failure requiring hospitalization, and coronary revascularization/angioplasty/stent
- Adverse events consistent with hypertension (see protocol section 8.4.6)
- Elevated serum aspartate aminotransferase (AST) or alanine aminotransferase (ALT) lab value requiring that study drug be temporarily withheld or permanently discontinued
- Neoplasms

Treatment listings will include the treatment arm, start and stop dates of the AE, and days on study relative to the day of first dose of study treatment. A Treatment related AE is defined as an AE for which the investigator classifies the AE as being “Probably Related” or “Possibly Related” to study treatment on Adverse Event CRF. Missing relationship and severity (intensity) will be imputed per Section 4.2.3.

The following additional listings will be provided:

- Listing of deaths
- Listing of Serious TEAEs

- Listing of treatment-emergent AESIs
- Listing of TEAEs leading to withdrawal or Interruption of study treatment

Listing of all AEs with a flag for TEAEs and onset (Prior = prior to first dose of single-blind medication, Run-in = on or after first dose of single-blind medication but prior to first dose of double-blind medication, or Treatment = on or after first dose of double-blind medication.)

A listing of all medical history and pre-double-blind treatment adverse events with coded preferred terms belonging to the standard MedDRA query of hypertension will be created.

7.2. **Laboratory Evaluations**

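### The SAP never uses the symptomatic/asymptomatic mark collected for each urinary tract infection, so symptomatic infection is not reported separately by arm

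*SAP*

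**What the plan says.** **Definition.** Protocol 8.4.6 records an AE of UTI if both "the following criteria are fulfilled, regardless of subject symptoms". The two criteria are "a positive urine culture result with a bacteriuria count of" 10^5 CFU/mL or more, and "leukocyturia of" at least 5/hpf.

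**The mark.** For each event that meets the definition, "the investigator will record whether the UTI was" symptomatic or asymptomatic, on the AE eCRF. Clinically significant urine findings that "do not fulfill the above definition of a UTI, the findings should be recorded as AEs (eg, bacteriuria, leukocyturia") go under those other terms.

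**How cases are found.** Protocol Appendix 2 (10.2) sends a sample for urinalysis and culture "only if the urine dipstick tests positive for the presence of leukocytes, nitrites, or blood cells". Symptoms reported at any visit also prompt testing. Urinalysis is part of the laboratory panel, and Protocol Appendix 7 (10.7) schedules laboratory assessments for all men at Weeks 4, 12 and 24 after randomization.

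**Reporting.** SAP 7.1 names the category "Adverse events suggestive of cystitis or urinary tract infection (UTI" without dividing it. Table 9 of the SAP plans AESIs by preferred term (14.3.1.12), treatment-related AESIs by preferred term (14.3.1.13) and an AESI listing (14.3.1.20). Neither the SAP text nor its lists of tables, figures and listings mention the symptom mark.

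**The concern.** The protocol puts two kinds of event under one definition and collects the field that separates them. The SAP then leaves that field unused. A man who presents with infection and a man with no complaint, whose scheduled dipstick led to a positive culture with pyuria, add the same amount to the UTI count.

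The study rationale in the protocol synopsis cites this population's particular safety needs, with urinary retention as the example, and UTI is a named event of special interest. A reader of the study report will want to know whether more men on vibegron than on placebo had a clinical infection. Outputs produced as specified would not give that count by arm. If the pooled count did differ between arms, they would not show which kind of event was responsible.

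**Working it through.** The plan states no UTI rate, margin or comparison, so there is no figure of its own to reproduce. The main check is textual.

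**Step 1: does any other planned output separate the two kinds?**

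- *Maximum intensity (14.3.1.4).* Protocol Appendix 3 (10.3) defines Grade 1 to cover both asymptomatic events and mild symptoms. Grade therefore cannot stand in for the mark.
- *Grade 3 or higher, and serious events.* These pick out only the most severe cases and miss ordinary symptomatic infection.
- *Preferred-term tables.* Nothing in SAP 7.1 says that the mark enters coding or forms a table row.
- *Urine results.* SAP 7.2 sends dipstick and central urinalysis results to listings. Table 9 also has urinalysis summaries (14.3.2.3). Both concern laboratory values, not symptoms.
- *AESI listing (14.3.1.20).* The mark is not named among its contents. Even if shown, a by-subject listing is not a count by arm.
- *Contrast.* Hypertension, another event of special interest, has its own breakdowns by pre-existing and baseline hypertension (14.3.1.15 and 14.3.1.16).

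No planned output gives the number of men per arm with symptomatic UTI.

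**Step 2: what could pooling do to the comparison?**

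All UTI rates here are assumptions. The only input from the documents is 544 men per arm (Protocol 9.2, SAP 1.2.4). Let p be the placebo rate and v the vibegron rate, and assume that no man has both kinds of event, so that rates add.

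- Risk ratio = v / p
- Risk difference = v − p
- 95% half-width = 1.96 × √[p(1 − p)/544 + v(1 − v)/544]

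For the first row below: √[(0.0196 + 0.0384)/544] = 0.0103, and 1.96 × 0.0103 = 0.020.

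| Assumed events | Placebo | Vibegron | Risk ratio | Risk difference (points) | 95% half-width (points) |
|---|---|---|---|---|---|
| Symptomatic only | 2% | 4% | 2.00 | 2.0 | 2.0 |
| Plus asymptomatic 2% in both arms | 4% | 6% | 1.50 | 2.0 | 2.6 |
| Plus asymptomatic 4% in both arms | 6% | 8% | 1.33 | 2.0 | 3.0 |
| Plus asymptomatic 2% vs 4% | 4% | 8% | 2.00 | 4.0 | 2.8 |

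Other assumed symptomatic rates behave the same way when 0%, 2% and 4% asymptomatic events are added to both arms:

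- 1% vs 3%: risk ratio 3.00, 1.67, 1.40; half-width 1.7, 2.3, 2.8 points; difference 2.0 points throughout.
- 1% vs 2%: risk ratio 2.00, 1.33, 1.20; half-width 1.4, 2.2, 2.7 points; difference 1.0 point throughout.

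An equal background lowers the risk ratio and widens the interval without moving the expected risk difference. A background that follows the drug (last row of the table) leaves the risk ratio at 2.00 and doubles the difference.

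**The case against.** Three stronger readings are tempting. The documents support none of them.

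*A reader might infer that symptomatic infection goes unreported.* It does not. Events meeting the definition enter the overall, AESI and maximum-intensity tables and the listings, and those that qualify also enter the treatment-related, serious and Grade 3 or higher tables. What is missing is a separate count by arm. The SAP does not fully specify the columns of the AESI listing, so the mark may appear there.

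*A reader might infer that a positive dipstick, or bacteriuria alone, counts as UTI.* The dipstick only triggers further testing. Culture at threshold and leukocyturia are both required, and lesser findings are recorded under other terms. The protocol thus already does part of the separation.

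*A reader might infer that a drug effect is diluted and power lost.* That requires asymptomatic events to be common and unrelated to treatment. A mechanism working through raised residual urine gives no reason to spare asymptomatic events, and if they follow the drug, pooling does not dilute. SAP 7.1 presents adverse events as counts and percentages with no planned test for UTI, so there is no planned power to lose.

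It is also fair to say that exclusion criterion 14 removes active or recurrent UTI by symptoms or laboratory criteria, and that eligibility is rechecked before randomization, which should limit asymptomatic infection already present at entry. The residual-urine pathway is followed directly through SAP 7.5 and the urinary-retention AESI. The mark stays on the eCRF and could be tabulated later.

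These points limit the importance of the gap but do not close it. A later tabulation would be post hoc, whereas the row can be specified now from a field the protocol deliberately collects.

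**Conclusion.** The point holds as a gap in reporting. The SAP specifies no use of a field collected for each UTI, so symptomatic UTI is not reported separately by arm, and the UTI count mixes clinical infection with asymptomatic, culture-positive bacteriuria with pyuria. This rests on the text alone and on no assumed rate.

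The effect of the mixing on the comparison is unknown in size and conditional in direction. The figures above show the mechanism only. No statement about power should be drawn from them, and no primary, secondary or planned safety inference is affected. This is a cheap improvement.

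**What to change.** In SAP 7.1 and Table 9, add a UTI summary with three rows per arm:

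1. men with any UTI (the pooled count, kept);
2. men with at least one symptomatic UTI;
3. men with only asymptomatic UTI.

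Give each row a risk difference with 95% CI, labelled descriptive. Rows 2 and 3 add up to row 1 if the mark is complete; show any men who cannot be classified because a mark is missing. Show the mark in listing 14.3.1.20.

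The cost is a short SAP change and a few lines of programming from a field already on the AE eCRF. The downside is smaller counts and wider relative uncertainty in each row. The definition of a UTI adverse event, the testing schedule and all clinical rules stay as they are.

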7.3.1.1. Vital Sign Subgroups

The vital sign data for blood pressure and pulse rate will be summarized by subgroups that may be at a higher risk, in Table 8

Table 8: At Risk Subgroup for Vital Sign Summaries

Subgroup	Definition of At Risk Subgroup
Age	≥ 75 years
Pre-Existing Hypertension	Pre-Existing Hypertension will be based on medical history and/or baseline hypertension, as defined in Section 4.3.5
High BMI at baseline	$BMI \geq 35 \text{ kg/m}^2$
At Risk eGFR Group	$eGFR \leq 60 \text{ mL/min/SA}$

7.3.1.2. Categorical/Threshold Analysis

Categorical analyses (e.g. percentage of patients with an absolute change from baseline of ≥ 5 , 10, or 15 mmHg for blood pressure and ≥ 5 , 10, or 15 bpm for heart rate) of any post-baseline change and at 2 consecutive post-baseline visits timepoints.

The categorical analysis will be produced for the safety population and for subgroups that might be at a higher risk (e.g., pre-existing hypertension, older patients [$age \geq 75$ years], renal impairment [$\leq 60 \text{ mL/min/SA}$], and high BMI [$\geq 35 \text{ kg/m}^2$]), as well as their complements.

7.3.2. Orthostatic Blood Pressure and Pulse Rate (Part 1 only)

Blood pressure and pulse rate measurements are collected at Screening, Run-in, Baseline, Week 2 and 4 to assess for potential orthostatic vital sign changes. Triplicate measurements are

obtained for both sitting and standing blood pressure assessments at Hour 0 (pre-dose) and Hours 1, 2, 4, and 6 post-dose. A singular pulse rate is also obtained in sitting and standing positions at the same hourly timepoint. The average blood pressure of triplicates will be used for summary. Within each timepoint, orthostatic blood pressure and pulse rate will be derived by subtracting time-matched standing average values from sitting average values. Then time-matched change from Day 1 will be derived as follows:

- Step 1: calculate change from pre-dose at each visit

CFPre at baseline visit: (Baseline 1 hr – Baseline pre); (Baseline 2hr – Baseline pre)

(Baseline 6 hr – Baseline pre)

CFPre at Week 2 visit: (Week 2 1 hr – Week 2 pre); (Week 2 2hr – Week 2 pre)

(Week 2 6 hr – Week 2 pre)

CFPre at Week 4 visit: (Week 4 1 hr – Week 4 pre); (Week 4 2hr – Week 4 pre)

(Week4 6 hr – Week4 pre)

- Step 2: calculate time-matched from Day 1 by subtracting time-matched CFPr of Baseline visit from CFPr of Week 2 and Week 4

[(Week 2 1 hr – Week 2 pre) - (Baseline 1 hr – Baseline pre)]

[(Week 2 2hr – Week 2 pre) - (Baseline 2 hr – Baseline pre)]

...

[(Week2 6hr – Week2 pre) - (Baseline 6hr – Baseline pre)]

Observed SBP, DBP, and pulse rate will be summarized by treatment, visit and assessment time including corresponding change from baseline value. Baseline is the average of pre-dose measurement at Day 1. The following summary tables will be prepared for derived orthostatic SBP, DBP and pulse rate:

- Time-matched orthostatic parameters by treatment, visit and assessment time
- Time-matched change from Day 1 in orthostatic parameters by treatment, visit and assessment time
- Maximum CFB over 6 hours in orthostatic parameters by treatment and visit
- Average CFB over 6 hours in orthostatic parameters by treatment and visit

In addition, the following plots will be prepared for orthostatic vital sign parameters

- Line plot over time of time-matched change from Day 1 of orthostatic parameters
- Empirical cumulative distribution function of maximum CFB over 6 Hours

For SBP and DBP, the number and percentage of subjects with a decrease of ≥ 20 mmHg for SBP and ≥ 10 mmHg for DBP from sitting to standing position will also be presented by treatment, visit and assessment time. All orthostatic blood pressure and pulse rate measurements will be listed.

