4.3.4. Baseline and Change from Baseline

In general, the last recorded value on or prior to the date of randomization will serve as the baseline measurement for efficacy endpoints while the last recorded value prior to first double-blind dose of study treatment will serve as the baseline measurement for safety endpoints. The mean of multiple values will be used as baseline for the following situations:

- If multiple measurements are scheduled on the same baseline day (i.e., blood pressure)
- If multiple measurements are collected on the same baseline day without the time or “repeat” status to differentiate the records

For efficacy endpoints derived from the Bladder Diary, the baseline will be the average value over the diary days in the baseline analysis visit window.

Change from baseline will be calculated as the post-baseline value minus the baseline value. Percentage change from baseline will be calculated as the change from baseline divided by the baseline value, multiplied by 100. If either the baseline or post-baseline value is missing, then change from baseline and percentage change from baseline will be set to missing.

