14.3.1.20 Listing of TEAEs of Special Interest	SAF	
Safety Labs		
14.3.2.1 Hematology Laboratory Parameters	SAF	Include observed and CFB

Title	Population	Programming notes
14.3.2.2 Clinical Chemistry Laboratory Parameters	SAF	Include observed and CFB
14.3.2.3 Urinalysis Laboratory Parameters	SAF	Include observed and CFB
14.3.2.4 Summary of Other Laboratory Parameters	SAF	
14.3.2.5 Abnormal Classification of Hematology Laboratory Parameters	SAF	
14.3.2.6 Abnormal Classification of Clinical Chemistry Laboratory Parameters	SAF	
14.3.2.7 Abnormal Classification of Urinalysis Laboratory Parameters	SAF	
14.3.2.8 Abnormal Classification Summary of Other Laboratory Parameters	SAF	
14.3.2.9 Shift Table of L/N/H Classification for Hematology Laboratory Parameters	SAF	
14.3.2.10 Shift Table of L/N/H Classification for Chemistry Laboratory Parameters	SAF	
14.3.2.11 Maximum Post-baseline ALT and AST vs. Maximum Post-baseline Bilirubin	SAF	
14.3.2.12 Listing of Subjects who Potentially Met Hy's Law	SAF	

Title	Population	Programming notes
Concomitant Medication		
14.3.3.1 Non-OAB Concomitant Medication	SAF	
14.3.3.2 OAB Concomitant Medication	SAF	
Regular and Orthostatic Vital Signs		
14.3.4.1 Vital Sign Parameters	SAF	Include all observed and CFB
14.3.4.2 Vital Sign Parameter Change from Baseline Shifts at 3 Consecutive Visits	SAF	SBP, DBP and PR
14.3.4.3 Vital Sign Parameter Change from Baseline Shifts at Week 24	SAF	SBP, DBP and PR
14.3.4.4 Vital Sign Parameter Maximum Post-Baseline Change from Baseline	SAF	SBP, DBP and PR
14.3.4.5 Orthostatic Blood Pressure and Pulse Rate	SAF-Orth	
14.3.5.1 Time-Matched Change from Sitting to Standing Position in Orthostatic Blood Pressure and Pulse Rate	SAF-Orth	
14.3.5.2 Time-Matched Change from Day 1 in Orthostatic Blood Pressure and Pulse Rate	SAF-Orth	

Title	Population	Programming notes
14.3.5.3 Maximum CFB over 6 Hours in Orthostatic Blood Pressure and Pulse Rate	SAF-Orth	
14.3.5.4 Average CFB over 6 Hours in Orthostatic Blood Pressure and Pulse Rate	SAF-Orth	
14.3.5.5 Categorical Shift from Sitting to Standing in Blood Pressure	SAF-Orth	
Urodynamics		
14.3.6.1 Urodynamics Assessments	SAF-UDS	
Other		
14.3.7.1 Prostate Volume Measurements	SAF	
14.3.8.1 Uroflow Measurements	SAF	
14.3.9.1 Total IPSS score	SAF	
14.3.10.1 Physical Examination Shift from Baseline	SAF	

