14.3.5.4	Empirical Cumulative Distribution Function of Maximum Change from Baseline over 6 Hours to Week 2 and Week 4 Orthostatic Systolic Blood Pressure	SAF-Orth Week 2 and Week 4 CDF plots side-by-side on the same page
14.3.5.5	Empirical Cumulative Distribution Function of Maximum Change from Baseline over 6 Hours to Week 2 and Week 4 Orthostatic Diastolic Blood Pressure	SAF-Orth Week 2 and Week 4 CDF plots side-by-side on the same page
14.3.5.6	Empirical Cumulative Distribution Function of Maximum Change from Baseline over 6 Hours to Week 2 and Week 4 Orthostatic Pulse Rate	SAF-Orth Week 2 and Week 4 CDF plots side-by-side on the same page

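### The orthostatic pulse maximum in SAP 7.3.2 reports each man's smallest rise on standing, because pulse is derived as sitting minus standing and the maximum is signed.

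*SAP*

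**What the plan says.** The chain of definitions lies in the SAP.

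- **Sign.** Section 7.3.2 uses one rule for all three parameters: "orthostatic blood pressure and pulse rate will be derived by subtracting time-matched standing average values from sitting average values". The derived value is sitting minus standing.
- **Baseline.** The same section says "Baseline is the average of pre-dose measurement at Day 1".
- **Change.** Section 4.3.4 makes it signed: "Change from baseline will be calculated as the post-baseline value minus the baseline value".
- **Summary.** Section 7.3.2 opens its list with "The following summary tables will be prepared for derived orthostatic SBP, DBP and pulse rate" and includes "Maximum CFB over 6 hours in orthostatic parameters by treatment and visit". The plots include "Empirical cumulative distribution function of maximum CFB over 6 Hours".
- **Displays.** Table 14.3.5.3 carries the maximum for blood pressure and pulse together. Figure 14.3.5.6 is titled "Empirical Cumulative Distribution Function of Maximum Change from Baseline over 6 Hours to Week 2 and Week 4 Orthostatic Pulse Rate". Figures 14.3.5.4 and 14.3.5.5 do the same for systolic and diastolic pressure.
- **Direction.** Section 7.3.2 counts men whose pressure drops on standing by at least 20 mmHg systolic or 10 mmHg diastolic, so the direction of interest for blood pressure is explicit. There is no equivalent count or direction for pulse.
- **A different label.** Table 14.3.5.1 is titled "Time-Matched Change from Sitting to Standing Position in Orthostatic Blood Pressure and Pulse Rate".

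Neither Section 7.3.2 nor the display lists describe the maximum as absolute, as worst-case, or as specific to a parameter.

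**The concern.** On standing, blood pressure may fall and pulse may rise. One sign applied to both puts the two responses on opposite sides of zero, so one signed maximum cannot be the most affected hour for both. With sitting minus standing, pulse is the parameter that loses.

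Serial orthostatic measurement is what distinguishes Part 1, and a maximum over 6 hours is useful mainly because it can show a short-lived effect that an average would dilute. If the pulse maximum is taken at the least-affected hour, the table and the cumulative distribution plot could look reassuring while a transient rise is present. It would also sit oddly with SAP 4.2.4.2, which selects the worst value when several safety values fall in one window.

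**Working it through.** The documents give no figure for these summaries, so there is none to reproduce. The check is algebra, then an example and a simulation on assumed values.

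**1. Algebra.** Let R(t) be the standing rise, standing minus sitting, at hour t, and R(0) its Day 1 pre-dose value. Section 7.3.2 defines O(t) = sitting − standing = −R(t). With Section 4.3.4:

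CFB(t) = O(t) − O(0) = −[R(t) − R(0)]

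max over t of CFB(t) = −min over t of [R(t) − R(0)]

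The signed maximum is minus the smallest rise relative to baseline. This is an identity. It needs no assumption about noise or about correlation between hours.

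**2. Worked example (assumed readings).** Sitting pulse is 70 bpm throughout and sitting SBP is 130 mmHg throughout.

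| | Day 1 pre-dose | 1 h | 2 h | 4 h | 6 h |
|---|---|---|---|---|---|
| Standing pulse | 76 | 82 | 100 | 84 | 78 |
| Sitting − standing | −6 | −12 | −30 | −14 | −8 |
| CFB | – | −6 | −24 | −8 | **−2** |
| Standing SBP | 128 | 120 | 105 | 118 | 127 |
| Sitting − standing | 2 | 10 | 25 | 12 | 3 |
| CFB | – | 8 | **23** | 10 | 1 |

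The bold cells are the reported maxima. For SBP the maximum is 23 mmHg at hour 2, the worst hour. For pulse it is −2 bpm at hour 6, the least-affected hour; the 24 bpm excess rise at hour 2 does not appear. If the visit's own pre-dose reading also counts (Section 7.3.2 does not say) and equals the Day 1 value, the reported pulse maximum is 0.

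**3. Sensitivity (simulation, 200,000 men per setting).** Assumptions: four post-dose hours (1, 2, 4, 6), independent normal noise with the same SD at each hour and at baseline, and an excess standing rise at hour 2 only.

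| Noise SD (bpm) | Excess (bpm) | Mean maximum | Mean minimum | Maximum taken at hour 2 |
|---|---|---|---|---|
| 4 | 0 | 4.12 | −4.10 | 24.9% |
| 4 | 5 | 3.49 | −6.28 | 4.5% |
| 4 | 10 | 3.39 | −10.22 | 0.3% |
| 6 | 0 | 6.19 | −6.16 | 25.0% |
| 6 | 5 | 5.39 | −8.03 | 8.7% |
| 6 | 10 | 5.12 | −11.17 | 2.1% |

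For a 10 bpm excess:

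- SD 4: the maximum moves 4.12 − 3.39 = 0.73 bpm; the minimum moves 10.22 − 4.10 = 6.12 bpm.
- SD 6: the maximum moves 6.19 − 5.12 = 1.07 bpm; the minimum moves 11.17 − 6.16 = 5.01 bpm.

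The shift in the maximum also has a ceiling. Once the affected hour is never selected, the maximum is that of the other three hours, with expectation 3/(2√π) = 0.846 SD: 0.846 × 4 = 3.38 and 0.846 × 6 = 5.08. The simulated 3.39 and 5.12 are already about there, so a larger effect at that hour would hardly move the statistic further.

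**The case against.** The algebra is hard to dispute; the scope can be disputed, and several limits stand.

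- **Blood pressure is right as written.** A reader might infer that the SBP and DBP maxima fail too, since the title of Table 14.3.5.1 could be read as standing minus sitting. The documents do not support that. The title belongs to another table and names a comparison, while Section 7.3.2 gives an explicit derivation. The title is a labelling point only.
- **The named safety question is covered.** The adverse event of special interest in Protocol 8.4.6 is orthostatic hypotension, and the threshold counts of blood pressure falls do not depend on the maximum.
- **Pulse remains visible elsewhere.** Section 7.3.2 also gives pulse by visit and hour, time-matched change from Day 1 by hour, the average over 6 hours, a line plot and full listings. What is missing is any other worst-hour or threshold summary of pulse for each man.
- **No decision is shown to rest on this output.** A reader might infer that the review before Part 2 was compromised. SAP 1.2.1 places the orthostatic criteria in the DSMB Charter, and SAP 2.1 refers to a separate DSMB SAP. The affected output is descriptive.
- **It is not a fixed bias between arms.** A reader might take the gap between the largest and smallest hourly values as the size of the error. Under pure noise that gap arises equally in both arms and cancels in the comparison, and the documents give no SD from which to size it. An effect uniform over the post-dose hours would shift the maximum by its full amount. The loss concerns effects confined to some hours.

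**Conclusion.** The point holds for pulse only. Followed as written, the SAP makes the pulse part of Table 14.3.5.3 and Figure 14.3.5.6 show each man's smallest standing rise relative to baseline. The cost is lost sensitivity to a rise confined to one or some post-dose hours: for a 10 bpm excess at one hour, the mean reported statistic moves by 0.73 to 1.07 bpm, against 5.01 to 6.12 bpm for the minimum, at assumed noise SDs of 4 and 6 bpm.

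The conclusion rests on reading the maximum as the ordinary signed one, which is what the text gives; an absolute maximum would lose direction for all three parameters. It also rests on a rise being the pulse direction of concern, which is general physiology and not stated in the SAP. The simulated sizes depend on the assumed SDs and independent hours; the selection of the wrong hour does not. No power, type I error or efficacy result is affected. This is a definite error in a planned safety summary, limited in reach, and worth correcting because the correction is nearly free.

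**What to change.** Keep the sitting-minus-standing derivation, since reversing it would disturb blood pressure outputs that already work.

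1. For pulse only, in SAP 7.3.2, Table 14.3.5.3 and Figure 14.3.5.6, replace the maximum with the minimum change from baseline over 6 hours. Label it as the largest increase from baseline in standing-minus-sitting pulse.
2. Label the SBP and DBP maximum in Table 14.3.5.3 and Figures 14.3.5.4 and 14.3.5.5 as the largest orthostatic fall relative to baseline.
3. State the sign in Table 14.3.5.1 so that its title agrees with Section 7.3.2.

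The cost is a few lines of SAP text, one change from maximum to minimum in the pulse derivation, and display labels. No new data are needed and no other analysis changes.
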